2. the development of an evidence-based and effective treatment offer for a patient group that currently lacks effective treatment offers and a treatment offer that may be able to complement stem cell therapy in the long term.

Objectives:

Main:

To examine if craniosacral therapy in chest, throat, neck, cranium and mouth , combined with specific exercises, can decrease xerostomia in people who suffer from this after radiation therapy and/or surgery in neck or mouth because of cancer in mouth or throat, by using a questionnaire "xerostomia after minimum 3 months" and comparing baseline results, with results after end of treatment and results 6 months following the last treatment.

Second

To examine if the intervention has any effect on other well-known late sequelae after treatment of cancer in mouth and neck, by asking if and how participants are experiencing these symptoms and comparing baseline results, with results after end of treatment and results 6 months following the last treatment.

Third objective

To examine, if there is any sideeffects or adverse events of the treatment

Design

This project is a pilot-study. It's a one-arm intervention study, with before and after comparisons. There is no masking(open level)

Measurement method

Main objective: The participants will fill in the Danish questionnaire named "Xerostomia questionnaire after minimum 3 months".

The questionnaire will be filled in on the treatment day, before starting the treatment, on the 5.(and last time of treatment, before starting the treatment, and as follow up, 6 month after the treatment.

The participants will be alone, completing the questionnaire.

Other monitoring

Second objective (other late sequelae)

Participants will be contacted by phone the week before starting the treatment and interviewed about, which late sequelae they are experiencing – this will be written down in their journal and will be read aloud so they can confirm. The therapist will ask then about experiencing any changes in the late sequelae mentioned before start of treatment the last time of treatment, and at 6 month following up meeting.

Participants are asked if they are experiencing following late sequelae: dry mouth, obstipation, lymphedema, tinnitus, difficulty swallowing, tense/stiff neck, problems with respiration, stiff jaw, difficulty with speaking, fatigue, difficulty sleeping and pain and mental well-being

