. These late sequelae are chosen by reading results from a questionnaire about late sequelae fulfilled by members of: "Danish Network for Mouth and Throat Cancer" – a community of people who have been through treatment of cancer in throat and mouth.

Participants are also asked if they have any other late sequelae.

Third objective(side effects)

Participants are at the first treatment session receiving a diary to note if they have any side-effect after treatment. At each session the therapist will ask if the participant has been experiencing any side effects and these will be noted in the participant journal and combined together so that the results contain a total overview of experienced side effects

Intervention:

The participants will receive 50 minutes of treatment of craniosacral therapy once a week in 5 weeks. The treatment will follow the protocol "avenue of expression" and step 2c and 2c in "Ten step protocol". See appendix (1)

Statistical considerations

The participants filled in the danish questionaire " Xerostomia questionnaire after minimun 3 months". The questionnaire includes a VAS xerostomia scale 0-10 (10 is worst)

The remaining 14 questions were phrased "how much does [question subject] bother you:" (translated from Danish)

not at all (1) - a little (2) - some (3) a lot (4) very much(5)

The final question(number 15) were:

"How would you feel, if you had to live the rest of your life, with the symptoms you have now?:"
enjoyable(1), very satisfied (2) neither satisfied ore unsatisfied(3), very unsatisfied(4), terrible(5)
the sum of points from the 15 questions gives an overall score.

The remaining 14 questions were phrased "how much does [question subject] bother you:" (translated from Danish)

not at all (1) - a little (2) - some (3) a lot (4) very much(5)

The final question(number 15) were:

"How would you feel, if you had to live the rest of your life, with the symptoms you have now?:"
enjoyable(1), very satisfied (2) neither satisfied ore unsatisfied(3), very unsatisfied(4), terrible(5)
the sum of points from the 15 questions gives an overall score.

This will give two scores:

the was-scale-score between 0-10 (10 is worst)

and the score for the remaining questions between 15 – 75 (75 is best)

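### Other late sequelae: the only question with stated follow-up times covers sequelae already named, so new ones are not prompted for as written

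*Protocol*

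**What the plan says.** The second objective in the protocol (Objectives) is to see whether the intervention affects other known late sequelae, "by asking if and how participants are experiencing these symptoms and comparing baseline results, with results after end of treatment" and with results at six months.

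The procedure is under Other monitoring, Second objective:

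- In the week before treatment, participants are telephoned and "interviewed about, which late sequelae they are experiencing". The answers are written in the journal and read back for confirmation.
- For follow-up: "The therapist will ask then about experiencing any changes in the late sequelae mentioned before start of treatment the last time of treatment". The same sentence adds the six-month meeting.
- A checklist comes next: "Participants are asked if they are experiencing following late sequelae: dry mouth, obstipation, lymphedema, tinnitus, difficulty swallowing", and so on through 13 items. No time is given.
- Then the open question: "Participants are also asked if they have any other late sequelae". Again no time is given.

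Side effects belong to the third objective and are collected separately: "Participants are at the first treatment session receiving a diary to note if they have any side-effect after treatment", and "At each session the therapist will ask if the participant has been experiencing any side effects". The diary has no stated end date. The Design section describes a "one-arm intervention study, with before and after comparisons", without masking.

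**The concern.** The objective asks both whether and how symptoms are experienced at three times. That calls for the same enquiry at each time. The procedure with stated times does something narrower: it asks which sequelae are present once, before treatment, and afterwards asks about change in those.

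A set of symptoms chosen because they were present at baseline can shrink but cannot grow. If a follow-up question prompts only for that set, resolutions enter the record and new onsets do not. The before-after comparison can then look better than the participants' actual course.

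No control group is there to show the same drift. The protocol's answer to having no control group, in Statistical considerations, is to require at least two years since cancer treatment. That rule addresses natural healing; it does not affect which questions are asked at follow-up. If new sequelae are not asked about, an analysis cannot restore the missing answers.

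**Working it through.** The protocol gives no figure to reproduce here, so the check is to set the stated questions side by side.

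| Question | Stated time | Scope |
|---|---|---|
| Telephone interview | Week before treatment | Which sequelae are present |
| Question about changes | Last treatment; six-month meeting | Sequelae already mentioned |
| Checklist (13 items, counting pain and mental well-being separately) | None | Each listed sequela |
| Open question | None | Any further sequela |
| Side-effect diary | Handed out at first session; no end stated | Side effects |
| Side-effect question | Each of the 5 sessions | Side effects |

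**Step 1: what the timed questions can record.**

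- Sequela named at baseline: resolved, improved, unchanged and worse are all recordable at both follow-ups.
- Sequela absent at baseline: no timed question in this outcome prompts for it at either follow-up.

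**Step 2: does another parsing help?** The follow-up sentence lacks punctuation. It could mean that changes are asked about at three times, including before treatment. That alters the times but not the scope, which is still the sequelae mentioned.

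**Step 3: do other routes fill the gap?** Partly. A new complaint during the five weeks may be noted as a side effect, but under a different objective and only if the participant sees it as one. No side-effect question is stated for the six-month meeting. Advice to contact a doctor (Risks, Side effects, disadvantages) does not feed this outcome.

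**Step 4: contrast within the protocol.** For the xerostomia questionnaire, Measurement method and Statistical considerations both say that it is completed at all three times. No such statement is made for the checklist or the open question.

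**Step 5: direction, with assumed numbers.** Suppose a participant has 6 listed sequelae at baseline and, with no treatment effect, one resolves and one new one appears.

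- True count at follow-up: 6 − 1 + 1 = 6, a change of 0.
- Count from the literal procedure: 6 − 1 + 0 = 5, a change of −1.
- Count if the full list is repeated: 6, a change of 0.

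If no new sequela appears, the literal procedure and the full list agree. The error comes only from new onsets that go unasked. The documents give no onset or resolution rates, so this shows direction and not size.

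**The case against.** The best counter-argument is that nothing confines the checklist or the open question to baseline. Both come directly after a sentence that covers the last treatment and the six-month meeting, and the objective's own wording suggests that the same enquiry is meant each time. An interview guide may say so. On that reading nothing is lost. This stands: the defect is a schedule that is unstated for two questions and too narrow for the third, not a rule against asking about new symptoms. It does not remove the point, because the one rule that has follow-up times is limited to sequelae already mentioned. Which questions are asked and when is data collection that the protocol itself sets out, so it is not a matter left to an analysis plan.

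A reader might infer more than the text supports:

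- *That the procedure can record only improvement.* It cannot be read so. The question is about any changes, so worsening of a named sequela is recordable.
- *That all new complaints are lost.* The diary and the question at each session may catch some during treatment. The gap is clearest at six months.
- *That the number of questions left unasked measures the bias.* It would measure coverage only, and it depends on how many sequelae each participant named, which is not given.

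It is also fair to say that participants are at least two years past cancer treatment, and nothing in the protocol suggests that new sequelae are common. Nothing excludes them either: the stable state cited in Statistical considerations concerns dry mouth.

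**Conclusion.** The point holds as a minor one on a secondary, descriptive outcome. Followed literally, the timed procedure does not prompt at follow-up for a sequela absent at baseline, which fits poorly with an objective that asks whether symptoms are experienced at three times. Any resulting error leans toward apparent improvement.

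Its size is unknown. It is zero if the full list is in fact repeated at all three times, or if no new sequelae arise. The conclusion rests on reading the follow-up sentence as limited to sequelae already mentioned, which is its natural sense under either parsing, and on the checklist and open question not being repeated, which the protocol leaves open. The main xerostomia outcome is not affected.

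**What to change.** State under Other monitoring that the same checklist and the same open question are asked, in the same words, in the telephone interview before treatment, at the last treatment and at the six-month meeting. State that new, worsened, unchanged, improved and resolved sequelae are all recorded and reported.

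The protocol mixes past and future tense (for example in Statistical considerations and Hygiene), so some contacts may already have taken place. If so, ask the full list at those that remain, and report which questions were asked at which time.

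The cost is a few extra minutes at contacts already planned. No extra visit, staff or instrument is needed.

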Appendix section

Appendix 1

Treatment protocol Xerostomi

- anamnesis and introduction to the treatment. Here I made an oral agreement with the participant that they can ask me to stop the treatment at any time. I will also ask for consent to start the treatment in another bodily area than mentioned in the protocol, if I find that it is necessary.

Physical examination:

I will examine the cranial rhythm of heels, ankles, thighs, the pelvis, the ribbs, the shoulders, in the three global cranial hand positions, and the temporal hand position with a technique intended for listening for this rhythm.

I will do an arching to find energy cysts

All findings are documented in the journal.

Treatment

In every session I will start with a stillpoint at the feet.

I'll go through the protocol as far as I can during the time available, and continue in the next session.

Diaphragm with diaphragm handgrib

- diaphragm -

- Thoracic inlet
 - with diaphragm handgrib
- Infrathyroid muscles
 - with diaphragm handgrib
- os hyoideum and retrohyoid tissue
 - with diaphragm handgrib
- c1 og c2 (1 gram technique)
- treatment of the cranium in 5 steps:
 - 1: melt in the suboccipital tissue
 - 2: platform technique
 - 3: 5 grams traction of occiput in the direction of the cranium starting from atlas
 - 4 : decompression technique of the occipital condyles
 - 5: 5 grams dural traction

Cranial treatment

- frontal lift
- parietal lift
- sphenoidal compression-decompression

- temporal unilateral og bilateral ear-pull technique
- os mandibularis compression – decompression
- os nasalis technique
- os zygomaticus og processus pterygoideus – decompression techniques
- soft-tissue-technique upper and lower lip
- os maxillaris technique
- os vomer technique
- os palatinum technique
- roof of the mouth technique
- fascial glide of suprahyoid tissue
- tongue technique
- treatment of teeths and gums
- technique for re-stabilisation :
- Os maxillaris technique– in flexion and extension
- os mandibularis technique – compression and decompression
- os sphenoidalis technique – compression and decompression
- os temporale (earpull technique)
- cranial base technique

- CV4-technique

After each session I will retest the cranial rhythms . Test results and treatment is documented in the journal.

Finish the treatment with conversation, questions etc, and with information about expected side effects of the treatment.

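### The second objective promises a before-after comparison of other late sequelae, but no graded, like-for-like measure is specified and the treating therapist asks about change

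*Protocol*

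**What the plan says.** Under Objectives (Second), the Protocol says it will examine the other late sequelae "by asking if and how participants are experiencing these symptoms and comparing baseline results, with results after end of treatment", and again with results 6 months after the last treatment.

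Under Other monitoring (Second objective), it fixes the procedure:

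- **Baseline.** In the week before treatment, participants are phoned and "interviewed about, which late sequelae they are experiencing". On the answers, "this will be written down in their journal and will be read aloud so they can confirm".
- **Follow-up.** "The therapist will ask then about experiencing any changes in the late sequelae mentioned before start of treatment", on two occasions: "the last time of treatment, and at 6 month following up meeting".
- **Items.** "Participants are asked if they are experiencing following late sequelae", followed by 13 named items, of which dry mouth is the first, and a question about any further ones.

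No response scale is given for these items. For the main outcome, the Measurement method section says "The participants will be alone, completing the questionnaire", and Statistical considerations gives graded 1-5 answers and a 0-10 scale, collected at all three times. Design states that the study has one arm and no masking.

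**The concern.** Comparing baseline with two later times needs the same quantity recorded at each. Here the baseline is a list of symptoms and the follow-up is a recalled judgement of change. The judgement is given in conversation to the person who delivered the treatment, in an open study with no control group.

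Two things are at stake. First, a reported improvement in, say, fatigue or pain cannot be sized, and a large change cannot be told from a slight one. The pilot is meant to prepare a larger randomised study, and for these symptoms it would supply neither an effect size nor a measure of spread. Second, this way of asking invites favourable answers. The protocol takes a precaution against that for the main outcome and states none here.

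The protocol itself fixes this method of collection. It is not a matter left to an analysis plan, and no analysis plan could recover a grade that was never recorded.

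**Working it through.** No arithmetic beyond a count applies; the check sets the procedures side by side.

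| | Promised (Objectives, Second) | Stated procedure (Other monitoring) | Main outcome, for contrast |
|---|---|---|---|
| Baseline | whether and how symptoms are experienced | list of symptoms present, by phone, confirmed by the participant | scored questionnaire |
| Last session and 6 months | the same, for comparison | question about change in the symptoms mentioned | same scored questionnaire |
| Response scale | not stated | none stated | 1-5 items and 0-10 scale |
| Who collects | not stated | the therapist at follow-up; the baseline caller is not named | participant alone |

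**Step 1: what can be compared.** The baseline gives presence; the follow-up gives perceived change. From these one can classify each baseline symptom as gone, better, unchanged or worse. One cannot subtract a baseline severity from a later severity, because the procedure calls for neither.

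**Step 2: one-sidedness.** Follow-up is tied to symptoms already mentioned. If a participant names k symptoms at baseline, the number still present at follow-up can only be k or fewer. A count of symptoms can therefore fall but not rise, whatever the treatment does. The side-effect diary and the side-effect question at each session might pick up a new complaint, but they serve the third objective and record it as a side effect.

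**Step 3: how many items.** The list is dry mouth, obstipation, lymphedema, tinnitus, swallowing, neck, respiration, jaw, speaking, fatigue, sleep, pain and mental well-being: 13 items. Dry mouth is the main outcome and is rated by the questionnaire at all three times. That leaves 13 − 1 = 12. The figure is an upper limit, because the subjects of the 14 bother questions are not shown and some may overlap with the list.

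**Step 4: who asks, and over what interval.** The follow-up question is put by the therapist. Appendix 1 is written in the first person by the one giving treatment ("I'll go through the protocol as far as I can during the time available"), and no second therapist or independent interviewer is mentioned. The phone call falls in the week before five weekly sessions, so the participant looks back about 5 weeks at the last session. At the 6-month meeting it is about 7 months (roughly 5 weeks plus 6 months).

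**The case against.** The strongest case on the other side has five parts.

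- **A comparison is still possible.** This stands. A reader might infer that the promised baseline comparison cannot be made at all. The documents do not support that: the tally in Step 1 is feasible, and the objective's wording allows descriptive notes on how a symptom is experienced. What cannot be formed is a graded, like-for-like difference.
- **The baseline is written down and confirmed.** This stands in part. The journal entry limits error about which symptoms were present. With no grade recorded, it does not limit error about how bad they were.
- **Some symptoms may be rated elsewhere.** This stands. A reader might infer that no severity rating exists for any of the 13 items. That is wrong for dry mouth and cannot be established for the rest while the question subjects are not shown.
- **The item list might be asked at every visit.** The text does not say when the list is gone through, but the only follow-up question it states is about change. Even if the list were repeated, the result would be presence or absence, without a grade.
- **This is a secondary aim of a small pilot.** This stands as to weight. The protocol already urges caution in generalising its results. That caution rests on the group being small and heterogeneous, not on how these symptoms are measured.

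**Conclusion.** The point holds in limited form. For the other late sequelae the Protocol specifies no graded measure repeated in the same way at the three times. The follow-up information is a report of change elicited by the unmasked treating therapist and confined to symptoms mentioned at baseline. Up to 12 listed symptoms are affected, at both follow-up times.

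The bias probably favours the treatment, but its size cannot be derived from the document. It would go too far to say that participants will report improvement whether or not anything changed; the design makes such answers likelier and gives no means of checking them.

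The conclusion rests on three readings: that the stated follow-up question is the whole follow-up measurement, that the therapist who asks is the one who treats, and that no scale is used where none is stated. The main outcome is not touched. Listing dry mouth among the other sequelae is an overlap to tidy up, not a source of bias in itself. The change is worth making, but the study's main question does not depend on it.

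**What to change.** Add a one-page form, completed alone together with the xerostomia questionnaire at the same three times.

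- Rate every listed sequela at each time, whatever the baseline answer, on the 1-5 bother scale already in use. Reword mental well-being so that it fits that scale.
- Keep the open item for further sequelae, and ask it each time so that new symptoms can appear.
- Leave dry mouth to the main questionnaire.
- Report within-person change per symptom from baseline to each follow-up.

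The phone interview can stay for history taking.

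**Cost.** One extra page and a few minutes per participant on three occasions when a form is being completed anyway; no extra assessor. The study remains open and uncontrolled, so expectation effects are reduced but not removed.

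**If the data are already collected.** Parts of the Protocol are written in the past tense, so this may be the case. The form is then no longer an option. The report should state that the results for the second objective are unrated, therapist-elicited reports of change in symptoms named at baseline, and should draw no conclusion on effect from them.

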- If I during my journal procedure of my participant finds any signs of active disease, I will send them to their doctor and do not start my treatment before the doctors approval.

Risks, Side effects, disadvantages (long and short term)

Serious sideeffects of craniosacraltherapy is very seldom. When I was going to apply to "The central Denmark region Committees on health research ethics" for permission to carry out the project, they demanded a study of cases of serious side effects after craniosacral therapy, which made me make some extra exclusion criteria to this study. There is a single case where a person who was pregnant and had fallen had a spontaneous abortion after treatment. There are also a few cases where people who have been exposed to serious head or neck trauma have had side effects that required medical attention. Therefore, pregnancy and serious head/neck trauma are contraindicated in this project. In addition, there are a number of precautionary contraindications that are taken into account to avoid serious side effects. Read more under exclusion criteria.

Participants are instructed to contact their doctor if they experience anything concerning during the trial.

Any serious side effects will result in immediate cessation of the trial, and will of course be reported.

Commonly occurring/ not serious sideeffects

It is common for all types of patients to experience temporary fatigue, dizziness, flu symptoms, aches and pains, and increased digestive activity. It is also common to experience temporary emotional fluctuations. Since I have not treated many people with late effects of cancer, I do not know if they will have any other common late effects than the general population. Therefore it is a goal in this study to list any side-effects in this study.

Hygiene:

Since the participants belong to a group of people who are particularly vulnerable to infections and since the experiment was conducted during Covid times, face masks will be used during treatment and gloves are used when treating the mouth.

The table is disinfected between each treatment.

Gdpr

As this experiment takes place in Denmark, which is a member of the EU, there are a number of rules according to GDPR that must be observed. These are ensured in cooperation with "The central Denmark region Committees on health research ethics"

Economy:

sponsor/collaborators:

No sponsors - this study is self-financed

collaborators:

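### The safety objective includes adverse events, but its diary and session question collect only what participants call side effects, so unexpected events, short-lived worsening and events after session five can be missed

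*Protocol*

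**What the plan says.** The Protocol's Objectives section states the third objective as "To examine, if there is any sideeffects or adverse events of the treatment".

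Two tools serve it, both described under Other monitoring, Third objective. One is a diary handed out at the first session: participants are "receiving a diary to note if they have any side-effect after treatment". The other is oral: "At each session the therapist will ask if the participant has been experiencing any side effects". Answers are noted in the journal and pooled "so that the results contain a total overview of experienced side effects".

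The second objective, in the same section, follows symptoms that participants already have. Before treatment they are interviewed on 13 named late sequelae and asked an open question about others. Afterwards, "The therapist will ask then about experiencing any changes in the late sequelae mentioned before start of treatment the last time of treatment". The question is repeated half a year later, when participants return for follow-up.

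The paragraph on common, non-serious side effects says: "It is common for all types of patients to experience temporary fatigue, dizziness, flu symptoms, aches and pains, and increased digestive activity". It adds temporary emotional fluctuation. It also says that the investigator has treated few people with late effects of cancer and does not know whether they react differently, and gives this as the reason for listing side effects in the study. Appendix 1 ends the treatment description "with information about expected side effects of the treatment".

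**The concern.** A side effect is by definition something the treatment caused. A question in those terms makes the participant judge cause before anything is written down. That suits confirming known reactions. It does not suit the stated purpose here, which is to learn whether this group has reactions not yet known. An infection or a new symptom that the participant does not connect with the treatment would leave no trace under the third objective.

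Participants in this study also start with long-standing symptoms, some of which appear on the expected list. A passing flare of an old symptom can reasonably be put down to the old condition.

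The pilot is meant to lead to a larger randomized trial, and its safety overview would inform that trial. An event never recorded cannot be recovered by later analysis.

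**Working it through.** The protocol gives no event rate, sample size or other figure for safety, so nothing can be recalculated. The check sets the objective beside each step that could record an event.

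| Step | What is asked | When | Does the participant have to judge cause? | Feeds the side-effect overview? |
|---|---|---|---|---|
| Diary | Side effects | From session 1; no collection or review described | Yes | Not stated directly |
| Session question | Side effects | Each of 5 weekly sessions | Yes | Yes |
| Sequelae question (second objective) | Any change in baseline symptoms | Last treatment and 6 months | No | Not stated |
| Xerostomia questionnaire | Dry-mouth scores | Before session 1, before session 5, 6 months | No | Not stated |
| Advice to contact own doctor | Anything worrying | During the trial | No | No return to the trial record described |

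Four things follow.

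1. **New, unexpected events.** The last three rows do not bring a new event into the safety record: two concern existing symptoms, and the third does not return to the trial. Only the diary and the session question remain, and both depend on attribution.

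2. **Short-lived worsening.** The protocol expects reactions to be temporary, and its ethics section places them in the days after treatment. With weekly sessions, session 5 falls 5 − 1 = 4 weeks after session 1. A flare after sessions 1 to 3 can have settled by the time the sequelae question is asked. Until then it is recorded only if called a side effect.

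3. **After the fifth session.** Asking about the period since the previous treatment is possible at sessions 2 to 5, which covers 4 of the 5 post-treatment periods. The fifth runs to the 6-month meeting, which is described for the sequelae question and the questionnaire. No side-effect question or diary review is mentioned there.

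4. **Linkage.** Fatigue and pain are on both the expected-effects list and the sequelae list. Emotional fluctuation plausibly matches mental well-being. Increased digestive activity and constipation are a loose match at best. No rule says whether a worsened sequela counts as a safety event, so the same complaint may be counted under either objective.

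**The case against.** The strongest reply is the second objective. A reader might infer that worsening of existing symptoms has no route to being recorded. The protocol does not support that. Fatigue, pain, constipation and mental well-being are all on the baseline list, and changes in them are asked about without reference to cause. The questionnaire likewise picks up worsening dry mouth. This answers the point for worsening still present at session 5 or at 6 months. It leaves transient worsening, new events and the missing link to the safety overview.

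A reader might also infer that the safety result must look milder than the truth. That goes too far. Telling participants what to expect may make them more likely to report fatigue or pain as a side effect, while long-standing symptoms may make them less likely to. The net effect for listed items could go either way. Appendix 1 does not say which effects participants are told about.

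Three further replies have some weight. The objective is itself limited to effects of the treatment, so the gap between objective and tools is narrower than the words adverse events alone suggest. Even so, relatedness is better judged after recording than used as the condition for recording. Neither the diary nor the Danish wording of the question is reproduced, and the protocol uses side effect loosely elsewhere, once for sequelae of cancer treatment. The actual forms may be broader than their description. Finally, the advice to see a doctor and the reporting of serious side effects offer some protection, but no step brings doctor contacts back into the trial record.

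**Conclusion.** The point holds in a limited form. The two tools for the third objective record an event only if the participant attributes it to treatment. Existing symptoms are followed without that condition, but at two time points only and with no stated link to the safety overview. Unexpected new events, transient worsening and events after session 5 can therefore be missed.

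The number of events lost cannot be derived. Under-reporting is the likely direction for events that are not on the expected list; for those that are, the direction is open. The protocol gives no symptom frequencies, so it cannot be said how many participants carry an overlapping sequela.

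The conclusion assumes that the diary and question are worded as the protocol describes them and that no unmentioned review takes place at 6 months. It does not affect the xerostomia outcome. It should be put right because finding unknown reactions is a declared aim and the change is small.

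**What to change.** - Word the diary heading and the therapist's question as: *any new symptom, or existing symptom that became worse, since the last contact, whatever the cause*, with date and duration.
- Ask it at the start of each session and again at the 6-month meeting, and review the diary for the period after session 5.
- Record first and judge relation to treatment afterwards. Report all events and those judged related separately.
- State that sequelae found to have worsened under the second objective count in the safety overview.

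The cost is one reworded heading, one reworded question, one extra question at 6 months, and a somewhat longer event list that will include unrelated events. If data have already been collected with the narrower wording, the report should describe its list as participant-attributed side effects and not as all adverse events.
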